
Microarray mRNA data have been collected from the skin biopsy in from different lesions on Day -5 to -3 (Baseline) and Day 28.
 
To compare the expression value for each probe set, the following mixed- effects model will be fitted to each probe set, with mRNA intensity (log2 scale) as the response variable.
 
The model will include:
 
 Fixed terms: Skin Type Random: Subject (in sas Random intercept /subject=subjid) 
Notes Group B: Skin type refers to uninvolved skin, baseline GSK2646264 lesion, baseline Placebo lesion, GSK2646264 lesion at day 28 and Placebo lesion at day 28
 
For each probe set analysed adjusted means with corresponding 95% CI and fold changes with corresponding 95% CI's will be outputted. The fold change is derived from the ratio of the back-transformed estimate of the difference (GSK2646264 – Placebo) between adjusted means.
 
Since the data will be log2 transformed prior to the analysis the lesion effects will be expressed as ratios after back transformation. These ratios can be converted from treatment ratios to fold change values as follows:
 
 If ratio ≥ 1 then fold change = ratio If ratio < 1 then fold change = $-1/\text{ratio}$
Model Checking

 Refer to Appendix 6: Model Checking and Diagnostics for Statistical Analyses.
Model Results Presentation

Back transformed baseline-adjusted means along with 95% CIs will be calculated for each skin type group. Additionally, following fold changes with 95% CI will also be presented:
 
 - GSK2646264 lesion at day 28 – Uninvolved Skin (skin area H) - Placebo lesion at day 28 – Uninvolved Skin (skin area H) - Baseline GSK2646264 lesion – Uninvolved Skin (skin area H) - Baseline Placebo lesion – Uninvolved Skin (skin area H)

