11.8.10. Pharmacodynamic Tables

Pharmacodynamic (and or Biomarker) : Tables					
No.	Population	IDSL / TST ID / Example Shell	Title	Programming Notes	Deliverable [Priority]
IFN mRNA signature					
5.1.	Safety	PD2	Summary of mRNA Expression of Inflammatory Gene Transcripts in Biopsy (Group B-Natural Lesions)	Summary by treatment group (Placebo, GSK2646264 and uninvolved skin) First variable for Type of CLE – include All. See Section 11.3.5 for list of genes and probe-sets to be summarised	SAC
5.2.	Safety	PD_T2	Summary of Adjusted Mean and Fold Changes in mRNA Expression of Inflammatory Gene Transcripts in Biopsies (Group B-Natural Lesions)	Summary by treatment group (Placebo and GSK2646264) See Section 11.3.5 for list of genes and probe-sets to be analysed Footnote: 'Comparison to placebo fold change' is the fold change on GSK2646264 relative to placebo in log ₂ intensity at day 28.'	SAC
5.3.	Safety	PD_T3	Summary of Adjusted Mean and Fold Changes in mRNA Expression of Inflammatory Gene Transcripts in Biopsies by Skin Type (Group B-Natural Lesions)	Summary by skin type See Section 11.3.5 for list of genes and probe-sets to be analysed Footnote: 'Comparison to uninvolved fold change' is the fold change on GSK2646264 relative to placebo in log ₂ intensity.'	SAC

Pharmacodynamic (and or Biomarker) : Tables					
No.	Population	IDSL / TST ID / Example Shell	Title	Programming Notes	Deliverable [Priority]
Other biomarkers					
5.4.	Safety	PD_T1	Summary of Cell Markers from Immunohistochemistry (Absolute and Change from baseline) (Group B-Natural Lesions)	Summary by lesion type (Placebo, GSK2646264 and uninvolved skin). Replace treatment title with 'Lesion type' First variable for Type of CLE – include All.	SAC
5.5.	Safety	PD_T1	Summary of Histopathology score and components in skin biopsies (Absolute and Change from baseline) (Group B-Natural Lesions)	Page by score type – e.g final score then component score summaries Summary by lesion type (Placebo, GSK2646264 and uninvolved skin). Include change from baseline column where applicable. Replace treatment title with 'Lesion type' First variable for Type of CLE – include All.	SAC

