11.8.11. Pharmacodynamic Figures

Pharmacodynamic (and or Biomarker) : Figures					
No.	Population	IDSL / TST ID / Example Shell	Title	Programming Notes	Deliverable [Priority]
IFN mRNA signature					
5.1.	Safety	PD_F1	Individual Subject Profiles for mRNA Expression of IFN Signatures in Skin Biopsies (Group B-Natural Lesions)	Symbol by subject id, column panel by treatment group (Placebo and GSK2646264) Symbol by subject Id. Line pattern by CLE type See Section 11.3.5 for list of genes and probe-sets to be summarised	SAC
5.2.	Safety	PD_F3	Adjusted Mean Intensities (95% CI) for mRNA Expression IFN Signatures in Skin Biopsies (Group B-Natural Lesions)	Y xais – log2 scale By treatment group (Placebo and GSK2646264) Jitter by treatment (i.e. do not overlay the mean error bars.)	SAC
5.3.	Safety	PD_F4	Adjusted Mean (95% CI) Fold Change in mRNA Expression of IFN Signatures in Skin Biopsies (Group B-Natural Lesions)	Page by Gene ID. X-axis - probeset ID Include band from FC -1 to 1, transparency 0.5 Footnote: 'Comparison to placebo' is the fold change on GSK2646264 relative to placebo in log ₂ intensity at day 28.'	SAC
5.4.	Safety	PD_F5	Individual Plot of mRNA Expression of IFN Signatures in Skin Biopsies by Skin Type (Group B-Natural Lesions)	Symbol by CLE type, column panel by skin type. X-axis – subject id Symbol by CLE type See Section 11.3.5 for list of genes and probe-sets to be summarised	SAC

Pharmacodynamic (and or Biomarker) : Figures					
No.	Population	IDSL / TST ID / Example Shell	Title	Programming Notes	Deliverable [Priority]
5.5.	Safety	PD_F6	Adjusted Mean Intensities (95% CI) for mRNA Expression IFN Signatures in Skin Biopsies (Group B-Natural Lesions)	Since only one timepoint, replace x-axis with skin type. Symbol by subject Id. Include individual raw values	SAC
5.6.	Safety	PD_F6	Adjusted Mean (95% CI) Fold Change in mRNA Expression of IFN Signatures in Skin Biopsies by Skin Type (Group B-Natural Lesions)	Page by Gene ID. X-axis - probeset ID By Skin Type – symbol by skin type Include band from FC -1 to 1, transparency 0.5 Footnote: 'Comparison to uninvolved' is the fold change on GSK2646264 relative to placebo in \log_2 intensity.'	SAC
Exploratory PD endpoints					
5.7.	Safety	PD_F1	Individual plot of cell markers from Immunohistochemistry (Group B-Natural Lesions)	Symbol by subject id, column panel by treatment group (Placebo and GSK2646264) Symbol by subject Id. Line pattern by CLE type Heading: [marker name and description]	SAC

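### SAP 8.3.2, skin-type mRNA model: the fold change is defined and footnoted as drug versus placebo although every planned contrast is against uninvolved skin, and the single-variance, single-correlation model leaves the calibration of those intervals unknown

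*SAP*

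**What the plan says.** SAP 8.3.2 specifies two mixed models for log2 mRNA intensity in Group B. The second, by skin type, has "Fixed terms: Skin Type" and "Random: Subject (in sas Random intercept /subject=subjid" and no other covariance term. The treatment model above it adds an unstructured covariance over visit.

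The factor has five levels: "Skin type refers to uninvolved skin, baseline GSK2646264 lesion, baseline Placebo lesion, GSK2646264 lesion at day 28 and Placebo lesion at day 28". Protocol 6.1 shows where they come from: lesions F and G are each biopsied at baseline and Day 28, and uninvolved area H once at baseline.

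On the fold change, the skin-type model says: "The fold change is derived from the ratio of the back-transformed estimate of the difference (GSK2646264 – Placebo) between adjusted means". A few lines later it lists four fold changes with 95% CIs, beginning with "GSK2646264 lesion at day 28 – Uninvolved Skin (skin area H"; the other three are also lesion states minus area H. SAP 2.4 lists the same four as exploratory comparisons, to be done if appropriate.

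The Table 5.3 footnote (SAP 11.8.10) explains "Comparison to uninvolved fold change" as GSK2646264 relative to placebo. The Figure 5.6 footnote (SAP 11.8.11) says that the comparison to uninvolved skin "is the fold change on GSK2646264 relative to placebo in" log2 intensity.

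Appendix 6 (SAP 11.6.1) applies to both models. It plans Kenward-Roger degrees of freedom, a normal plot and residuals against fitted values. It allows data-driven adjustments and names transformation as the remedy for departures.

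**The concern.** The contrasts with area H are the plan's modelled evidence on two questions: whether lesions differ from normal skin in the IFN signature at baseline, and whether treated lesions move towards normal skin by Day 28. Two things could mislead a reader of those results.

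First, a footnote that says drug relative to placebo, under a column of lesion-to-uninvolved ratios, names a different comparison. A large ratio between lesion and normal skin could be read as a drug effect.

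Second, a subject intercept alone treats F at baseline and F at Day 28 as no more alike than F and area H, and gives normal skin the same variance as lesions. Protocol 4.4 describes existing lesions as varied in stage and activity, and nothing in the documents supports equal variance for uninvolved skin. If either assumption fails, the pooled standard error can be wrong for exactly these contrasts.

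**Working it through.** **Labels.** Set side by side, the places disagree as follows.

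| Place | Comparison stated |
|---|---|
| SAP 2.4, comparisons for skin biopsies | four lesion states against area H |
| SAP 8.3.2, skin-type model, results list | four lesion states minus area H |
| SAP 11.9, shell PD_T3, column heading | against uninvolved |
| SAP 8.3.2, skin-type model, definition sentence | GSK2646264 minus placebo |
| SAP 11.8.10, Table 5.3 footnote | GSK2646264 relative to placebo |
| SAP 11.8.11, Figure 5.6 footnote | GSK2646264 relative to placebo |

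The definition sentence is the same as in the treatment model, where it is right. It appears to have been carried over.

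**Intervals.** The plan gives no variance, correlation or interval width for this model, so there is no figure to reproduce. Inputs from the documents: five biopsies per subject, subject intercept only, about 15 subjects in Group B. Assumed inputs: lesional SD 1; uninvolved SD *s* from 0.25 to 1; lesion-lesion correlation *r_LL* from 0.2 to 0.8; lesion-uninvolved correlation *r_LU* from 0 to 0.5.

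For complete data the residual variance estimates the mean variance minus the mean covariance. There are 6 lesion-lesion pairs and 4 lesion-uninvolved pairs, so

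- residual variance = (s² + 4)/5 − (6·r_LL + 4·s·r_LU)/10
- model variance of a contrast = 2 × residual variance / n
- true variance of a contrast = (1 + s² − 2·s·r_LU)/n

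Worked examples:

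- *s* = 1, correlations 0.7 and 0.2: residual = 1 − 0.50 = 0.50; model/true = 1.00/1.60 = 0.625; SE ratio √0.625 = 0.79.
- *s* = 0.5, 0.5 and 0.2: residual = 0.85 − 0.34 = 0.51; 1.02/1.05 = 0.971; SE ratio 0.99.
- *s* = 0.5, both 0.5: residual = 0.85 − 0.40 = 0.45; 0.90/0.75 = 1.20; SE ratio 1.10.

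Simulated coverage of the nominal 95% interval for Day 28 GSK2646264 lesion minus area H (n = 15, 20,000 data sets per setting):

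| *s* | *r_LL* | *r_LU* | model SE / true SE | coverage |
|---|---|---|---|---|
| 1 | 0.5 | 0.5 | 1.00 | 95.0% |
| 1 | 0.7 | 0.2 | 0.79 | 87.6% |
| 0.5 | 0.8 | 0.2 | 0.79 | 88.4% |
| 0.5 | 0.7 | 0.2 | 0.86 | 91.0% |
| 0.5 | 0.5 | 0.2 | 0.99 | 94.5% |
| 0.25 | 0.5 | 0.2 | 1.01 | 95.4% |
| 0.5 | 0.5 | 0.5 | 1.10 | 96.8% |
| 0.25 | 0.2 | 0.2 | 1.18 | 97.8% |

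An extreme setting (*s* = 1, 0.7 and 0) gives residual 1 − 0.42 = 0.58, 1.16/2 = 0.58 and SE ratio 0.76, with coverage a little below this range. In the settings re-run at n = 10 and n = 6, results barely change, so this is not a small-sample effect. A paired t interval for the same contrast held 94.7% to 95.3% in every setting run at all three sizes.

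**The case against.** A reader might infer that the intervals are too narrow. The documents do not support a direction. Under-coverage appears when lesions resemble one another much more than they resemble normal skin. With *s* = 0.5 and lesion-lesion correlation 0.5, the SE ratio passes from 0.99 to 1.10 as the lesion-uninvolved correlation rises from 0.2 to 0.5. The variance ratio does not settle it either: equal SDs gave both 95.0% and 87.6%, and an SD ratio of 0.25 gave both 95.4% and 97.8%.

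A reader might also infer that drug versus placebo would be computed in place of the four contrasts. The results list, SAP 2.4 and the PD_T3 column heading all show the right intention. That makes the definition sentence a drafting slip, but the sentence and footnotes are still wrong as written, and the footnotes accompany the reported results.

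Appendix 6 is a partial safeguard. Its residual plot could reveal unequal variance, and it leaves room for adjustment. It does not examine correlation, and the remedy it names is transformation of data already on the log2 scale. Kenward-Roger works within the stated covariance and does not repair a wrong one.

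Finally, a random intercept is a common default and the contrasts are exploratory and optional. That stands, and it limits the weight of the covariance point.

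**Conclusion.** The labelling error is certain from the text: one sentence and two footnotes name a comparison that none of the four listed contrasts makes.

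The covariance restriction is equally certain as a description of the model, but its consequence is conditional. Coverage was about 88% to 98% over the tabulated settings, all of which rest on assumed variances and correlations and on complete data. The supported conclusion is that calibration is unknown in either direction.

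For scale, SAP 11.3.5 lists 30 probe sets, so four contrasts give 120 intervals. About 6 would be expected to miss at 95% coverage (120 × 0.05), about 15 at 87.6% (120 × 0.124) and about 3 at 97.8% (120 × 0.022). No primary conclusion depends on these intervals.

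**What to change.** 1. In the skin-type model of SAP 8.3.2, redefine the fold change as lesion relative to uninvolved skin (area H). Make the same change in the Table 5.3 and Figure 5.6 footnotes. This is wording only. At the same time, remove the reference to baseline-adjusted means, since this model has no baseline term, and give shell PD_T3 rows for all five skin types in place of three.
2. Report each of the four contrasts as a within-subject paired difference from area H on the log2 scale, with a t interval on n−1 degrees of freedom, at least as a sensitivity analysis. An unstructured matrix over five skin types is not a practical substitute: it has 5 × 6/2 = 15 parameters per probe set, with about 15 subjects.

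The paired analysis has costs. At n = 15 the degrees of freedom fall from 4 × 14 = 56 to 14, and the multiplier rises from 2.00 to 2.14 (a factor of 1.07). Where the pooled SE was too small, intervals widen materially: 1.07/0.79 = 1.35 and 1.07/0.76 = 1.41, or about 35% to 41%. Where it was too large they can narrow slightly: 1.07/1.095 = 0.98. A subject also drops out of a contrast when either biopsy is missing, which matters because SAP 8.3.1 excludes samples that fail quality control and SAP 11.4.2 imputes nothing for mRNA.

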## **7.6. Biomarker(s)/Pharmacodynamic Markers**

### **7.6.1. Biomarker(s)/Pharmacodynamic measurements in Skin Biopsies**

For group A, two pre-dose biomarker / PD biopsies will be obtained at day 1, one from an uninvolved skin region on the back of the patient (skin area E), and one from PV lesion B. At day 28, post-treatment biomarker / PD biopsies will be obtained from the two remaining non-biopsied PV lesions A and C, one PV lesion treated with study drug and one PV lesion treated with placebo.

For group B, three pre-dose biomarker / PD biopsies will be obtained at day -5 to -3, one from an uninvolved skin region (H) and from both of the existing lesions F and G. Ideally, the uninvolved skin region biopsy should be located on the same anatomical body area close to the existing lesion biopsy. At day 28, post-treatment biomarker / PD biopsies will be obtained from both of the existing lesions F and G, one existing lesion treated with study drug and one lesion treated with placebo.

Details of biomarker / PD skin biopsy sample processing, storage and shipping procedures are provided in the Study Reference Manual (SRM).

Biomarker / PD biopsies will be evaluated histologically and by transcriptomic analysis.

Transcriptomic analysis will determine the effect of placebo and active treatment on IFN gene expression. Gene expression will be measured using microarray technology, and/or

alternative equivalent technologies, which facilitates the simultaneous measurement of the relative abundances of thousands of RNA species resulting in a transcriptome profile for a skin biopsy sample. Genes may include but are not restricted to: MX1, MX2, OAS1, OAS2, IFI44. The same samples may also be used to confirm findings by application of alternative technologies.

Histological assessments of the biopsies will explore changes in pharmacodynamic and disease biomarkers. Markers may include (but are not restricted to):

IFN proteins (such as MxA) to assess changes in IFN signalling

SYK protein levels (such as but not restricted to phospho-SYK and total SYK) to assess target engagement

Immune cell and immune cell marker expression (such as CD3+ T cells, CD20+ B cells, CD11c+ myeloid dendritic cells and CD68+ macrophages).

Pathological evaluation for general appearance using a histopathological disease activity score, scoring on parakeratosis, ballooning, necrosis, junctional inflammation and the extent of dermal infiltrate.

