2.4. Statistical Hypotheses

The primary objective of the study is to evaluate the safety and tolerability of repeat doses of a cream formulation of GSK2646264 in patients with CLE. No formal statistical comparisons will be conducted to assess this objective. If deemed appropriate to assess key efficacy and pharmacodynamic endpoints, the following exploratory comparisons may be conducted:

- Group B
 - GSK2646264 treatment vs. Placebo in natural CLE lesions

If deemed appropriate the following exploratory comparisons may be conducted for pharmacodynamic markers from the skin biopsies:

- Group B
 - Baseline GSK2646264 lesion vs uninvolved skin (skin area H)
 - Baseline Placebo lesion vs uninvolved skin (skin area H)
 - GSK2646264 lesion at Day 28 vs uninvolved skin (skin area H)
 - Placebo lesion at Day 28 vs uninvolved skin (skin area H)

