8.3.2. Planned Pharmacodynamic and Biomarker Statistical Analyses

Planned Statistical Analyses
Endpoint(s)

 • IFN mRNA signatures
Model Specification
Microarray mRNA data have been collected from the skin biopsy in both GSK2646264 and placebo

Planned Statistical Analyses

treated lesions on Day -5 to -3 (Baseline) and Day 28.

To compare the expression value for each probe set, the following mixed- effects model will be fitted to each probe set, with mRNA intensity (\log_2 scale) as the response variable.

Baseline is defined as the measurement taken pre-dose at baseline of each treated lesions (i.e lesion-specific baseline).

The baseline observation will be defined as an additional response measured on the same subject prior to application of the treatment. Then this observation is not affected by any of the effects included in the basic model for the response.

Visit	Trt	XTrt
Baseline	GSK2646264	NA
Baseline	Placebo	NA
Day 28	GSK2646264	GSK2646264
Day 28	Placebo	Placebo

The model will include:

- Fixed terms: Treatment (Xtrt: Placebo, GSK2646264, NA), Visit, Visit and Treatment (Xtrt) interaction
- Random: Subject (in sas Random intercept /subject=subjid)
- Repeated: Visit (in SAS Repeated visit / subject=subjid type=un)

For each probe set analysed adjusted means with corresponding 95% CI and fold changes with corresponding 95% CI's will be outputted. The fold change is derived from the ratio of the back-transformed estimate of the difference (GSK2646264 – Placebo) between adjusted means.

Since the data will be \log_2 transformed prior to the analysis the treatment effects will be expressed as ratios after back transformation. These ratios can be converted from treatment ratios to fold change values as follows:

- If ratio ≥ 1 then fold change = ratio
- If ratio < 1 then fold change = $-1/ratio$

Model Checking

- Refer to [Appendix 6](#) : Model Checking and Diagnostics for Statistical Analyses.

Model Results Presentation

- Back transformed baseline-adjusted means along with 95% CIs will be calculated for each treatment group. Additionally, fold changes between active and placebo in change from

Planned Statistical Analyses
baseline intensity will be calculated, along with 95% CI.
Endpoint(s)

 IFN mRNA signatures
Model Specification

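### The baseline lesion-versus-uninvolved mRNA difference is planned only as two contrasts split by the cream assigned later; adding a pooled contrast would estimate it more precisely from biopsies already taken

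*SAP*

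**What the plan says.** Protocol 7.6.1 sets out the Group B baseline sampling: "three pre-dose biomarker / PD biopsies will be obtained at day -5 to -3, one from an uninvolved skin region (H") and one from each of lesions F and G. Protocol 4.1 places randomisation 2 to 4 days after these biopsies. Protocol 6.1 labels the lesions by size (F the larger) and assigns active and placebo to them at random, 1:1.

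The second mRNA model in SAP 8.3.2 has one fixed factor with five levels: "Skin type refers to uninvolved skin, baseline GSK2646264 lesion, baseline Placebo lesion, GSK2646264 lesion at day 28 and Placebo lesion at day 28". Its only covariance term is "Random: Subject (in sas Random intercept /subject=subjid"). For each probe set the "following fold changes with 95% CI will also be presented": the Day 28 active and Day 28 placebo lesions against site H, then "Baseline GSK2646264 lesion – Uninvolved Skin (skin area H") and "Baseline Placebo lesion – Uninvolved Skin (skin area H"). SAP 2.4 lists the same comparisons, including "Baseline Placebo lesion vs uninvolved skin (skin area H"), and says that they may be conducted if deemed appropriate. Neither section plans a contrast that combines the two baseline lesions.

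The first mRNA model in the same section gives both baseline biopsies one common treatment code (NA), on the reasoning that "Then this observation is not affected by any of the effects included in the basic model for the response".

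**The concern.** When F and G are biopsied, no cream has been applied and no assignment has been made. What later distinguishes a baseline active lesion from a baseline placebo lesion is a random label. Their expected expression is therefore the same, and so is their expected difference from H.

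The plan reports that one difference twice, each time from one of the two baseline lesional biopsies per patient. SAP 11.3.5 lists 30 probe sets. For each of them, Table 5.3 and Figure 5.6 would show two estimates of one quantity that differ only by chance, each with a wider interval than one estimate from both lesions.

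At stake is the precision of a descriptive result: how far each transcript is raised in these patients' untreated lesions, and so how large a reversal a drug could show. With about 15 patients planned for Group B, that precision is worth having.

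**Working it through.** **Plan's own figure.** None can be reproduced. Protocol 9.2 states that there is no formal power or sample size calculation, and neither current document gives an interval width for these contrasts.

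**Inputs.** Per patient: two baseline lesional biopsies and one uninvolved biopsy (Protocol 7.6.1), plus two Day 28 lesional biopsies. n = 15 (Protocol 9.2), complete data. Covariance: a random subject intercept with common residual variance σ² (SAP 8.3.2). Correlations and SD ratios outside that model are assumptions, because the documents give none.

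**Step 1. Under the SAP's model.** The subject intercept cancels in each contrast.

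- Split (one baseline lesion − H): variance = σ²(1 + 1)/n = 2σ²/n. At n = 15, SE = 0.365σ.
- Pooled (mean of both baseline lesions − H): variance = σ²(1/2 + 1)/n = 1.5σ²/n. At n = 15, SE = 0.316σ.
- SE ratio, pooled to split: √(1.5/2) = 0.866, a reduction of 13.4%. Read the other way, each planned SE is 1/0.866 = 1.155 times the pooled SE.
- Equivalent size: 15 × 2/1.5 = 20 patients on the split contrast.
- Day 28 lesion − H: SE = 0.365σ whether or not the baselines are pooled.

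A mixed-model simulation at n = 15 (300 runs) gave a mean model-SE ratio of 0.867.

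**Step 2. Outside the SAP's model.** Let lesional SD = 1, SD of H = r, lesion-lesion correlation = a, and lesion-H correlation = b.

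- Split: n·Var = 1 + r² − 2br
- Pooled: n·Var = (1 + a)/2 + r² − 2br

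The grid is r = 0.5, 0.75, 1; a = 0.2, 0.5, 0.8; b = 0, 0.2, 0.4.

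| Case | r | a | b | Split | Pooled | SE ratio |
|---|---|---|---|---|---|---|
| Largest gain | 0.5 | 0.2 | 0.4 | 0.85 | 0.45 | 0.73 |
| Smallest gain | 1 | 0.8 | 0 | 2.00 | 1.90 | 0.97 |

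If b may not exceed a, the lower end becomes 0.79. Pooling is more precise at every grid point.

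**Step 3. Is the model's interval for the pooled contrast sound?** The random intercept gives lesion-lesion and lesion-H pairs the same covariance. With complete data, unit variances, correlation a among all four lesional biopsies and b between each of them and H, the expected residual mean square is 1 − (6a + 4b)/10.

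Take a = 0.8, b = 0.2. The mean square is 1 − 0.56 = 0.44.

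- Split: model variance 2 × 0.44 = 0.88 against a true 1.60 (both over n), so the model SE is √(0.88/1.60) = 0.74 of the true SE.
- Pooled: model variance 1.5 × 0.44 = 0.66 against a true 1.50, so the model SE is √(0.66/1.50) = 0.66 of the true SE.

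Simulated coverage of nominal 95% intervals at n = 15:

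| r, a, b | Split, SAP model | Pooled, SAP model | Pooled, per-subject differences |
|---|---|---|---|
| 1, 0.8, 0.2 | 0.85 | 0.81 | 0.95 |
| 1, 0.5, 0.4 | 0.94 | 0.93 | 0.95 |
| 0.5, 0.5, 0.4 | 0.96 | 0.97 | 0.95 |

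**Step 4. Price of the safer interval.** Per-subject differences leave 15 − 1 = 14 degrees of freedom, against 4 × 14 = 56 in the five-level model. The t multiplier rises from 2.003 to 2.145. If the SAP's model were exactly right, the per-subject pooled interval would still be 0.866 × 2.145/2.003 = 0.93 times the width of the planned split interval.

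**The case against.** The secondary objective is the drug's effect on the IFN signature, and the documents nowhere name a disease-versus-normal signature as something to estimate. The comparisons with H are exploratory and conditional, the probe sets are fixed in advance on past quality, and no decision rests on the baseline contrasts. With balanced data the pooled log2 estimate is simply the mean of the two planned ones, so only its interval is missing. All of that stands, and it keeps the point minor.

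Three stronger readings are tempting, and the documents do not support them.

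- *The split serves no purpose.* Each arm-specific baseline contrast pairs with the same arm's Day 28 contrast, so a reader can see where each arm's lesions start relative to uninvolved skin and where they end. The pair also shows chance imbalance, which is plausible with about 15 patients and two lesions ranked by size.
- *Half the lesional data are discarded.* Each planned baseline contrast uses one of the two baseline lesional biopsies per patient, but the Day 28 biopsies are lesional too and the residual variance uses all five. Because H enters both versions, the loss is about 15% in SE, well short of what halving suggests.
- *The two mRNA models contradict each other.* The first constrains the baseline in order to compare active with placebo, and its text also speaks of a lesion-specific baseline. The second describes five tissue states against H. Different parameterisations for different questions are not a contradiction. The first model shows only that the SAP already accepts a common baseline mean.

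The covariance objection also stands. In Step 3, adding the pooled contrast inside the SAP's model could yield a less reliable interval than the planned ones. That bears on how the interval should be computed; the pooled estimate itself is more precise at every grid point.

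**Conclusion.** The point holds as a modest loss of precision on one exploratory, conditional output. Both planned baseline contrasts estimate the same quantity by design, and no planned output estimates it from both lesions. Under the SAP's random-intercept model with complete data, each planned SE is about 15% larger than the pooled SE. Outside that model the true pooled-to-split ratio is 0.73 to 0.97 over the assumed grid, nearest 1 when a patient's two lesions are much alike.

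The equal expectation rests only on biopsy before randomisation and on random assignment of the two lesions, both stated in the protocol. The size of the gain rests on correlations and SDs that the documents do not give. The planned contrasts are not wrong.

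**What to change.** Keep the four planned contrasts. Add to Table 5.3 and Figure 5.6 one pooled baseline contrast per probe set: 0.5 × (baseline GSK2646264 lesion + baseline Placebo lesion) − uninvolved skin H, and list it in SAP 2.4 and 8.3.2.

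Take its interval from per-subject differences (mean of F and G minus H, on the log2 scale), or from a model that lets the lesion-lesion and lesion-H covariances differ. Do not rely on the single random intercept for this interval.

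The cost is one extra row per probe set and the fewer degrees of freedom shown in Step 4. A patient without all three baseline biopsies drops out of the per-subject version; the alternative model would retain that patient. No new sample is needed, and no other result changes.
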